### **5.2 SECONDARY ENDPOINT(S)**

#### **5.2.1 Key secondary endpoint(s)**

Not applicable.

#### **5.2.2 Secondary endpoint(s)**

##### **5.2.2.1 Secondary endpoints of the Phase Ia (dose-escalation portion) of the trial**

The secondary endpoints of the Phase Ia dose-escalation portion of the trial are:

- The following PK parameters of BI 754091 (if feasible) will be evaluated after the first and after multiple administrations of BI 754091:
  - $C_{max}$ : maximum measured concentration of BI 754091 in plasma
  - $AUC_{0-504}$ : area under the concentration-time curve of BI 754091 in plasma over the time interval from 0 to 504 hours
- Confirmed OR, defined as the best overall response of confirmed CR or PR according to RECIST v1.1 as assessed by the Investigator where the best overall response is the best time point response recorded from the first administration of BI 754091 until the earliest of disease progression according to RECIST v1.1, death or last evaluable tumor assessment before start of subsequent anti-cancer therapy, loss to follow-up or withdrawal of consent.
- Number of patients experiencing DLTs from the start of treatment until end of treatment (in all cycles) as assessed approximately every 3 weeks.

Table 5.2.2.1: 1      Details of confirmed best overall response according to RECIST 1.1 derivation rules

Overall response (time point 1)	Overall response (>=28 days from time point 1)	Confirmed BOR
CR	CR	CR
CR	PD	SD as long as >=39 days*, otherwise, PD
CR	NE/Missing	SD as long as >=39 days*, otherwise, NE
PR	CR	PR
PR	PR	PR
PR	SD	SD as long as >=39 days*, otherwise, PD
PR	PD	SD as long as >=39 days*, otherwise, PD
PR/SD	NE/Missing	SD as long as >=39 days*, otherwise, NE
SD	SD/PD	SD as long as >=39 days*, otherwise, PD
NE	NE/Missing	NE

\* after first treatment administration

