 - Another biopsy (optional) should be taken upon PD (according to RECIST v1.1 and iRECIST), if possible. An optional biopsy should also be taken if a patient has stable disease over 3 subsequent disease assessment periods.
- m Tumour assessments should be done according to RECIST v1.1 and iRECIST and should include CT/PET scans of the chest and abdomen and, if clinically indicated, imaging of any other known or suspected sites of disease (e.g., pelvis, brain) using an appropriate method (CT/PET scan or MRI). The same radiographic procedure must be used throughout the trial. In case of suspected (but not confirmed) bone metastasis at screening, tumour assessment at screening should include a bone scan. If bone lesions are already known or confirmed at screening, correlative imaging (X-ray or CT scan) should be performed. Correlative imaging should then be repeated at each tumour assessment (see Section 5.2.1 for more detail). Assessments will be performed by the Investigator at screening and every 2 cycles (6 weeks) for the first 6 months of treatment and once every 3 cycles (9 weeks) thereafter until PD or start of further treatment for disease, and at the discretion of the Investigator.
- n If the decision is made to permanently discontinue BI 754091 during a scheduled visit, the EOT visit assessments should be performed instead of the scheduled visit.
- o **Patients enrolled in Protocol Version 4.0 (expansion Cohort 4 and higher):** Additional overall survival (OS) and progression-free survival (PFS) follow-up visits after the 30-day safety follow-up visit will be performed once every 12 weeks at least (by telephone) until death, loss to follow-up, withdrawal of consent, or end of the whole trial. **Patients enrolled in Protocol Version 3.0 and earlier (expansion Cohort 1,2,3):** Additional PFS follow-up visits after the 30-day safety follow-up visit will only be performed for patients who did not progress on treatment. These will be performed once every 12 weeks at least (by telephone) until PD, introduction of a new anti-cancer treatment, death, loss to follow-up, withdrawal of consent, or end of the whole trial.
- p The patients will not be required to go to the clinic on Cycle 4 Days 2 and 15 and Cycle 8 Days 2 and 15.
- q Only patients completed the activity up to until the cut off date for the primary report. All remaining patients will undergo EOT and 30 days visits safety procedures only.

TABLE OF CONTENTS

TITLE PAGE	1

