6.2 DETAILS OF TRIAL PROCEDURES AT SELECTED VISITS

The procedures required at each trial visit in both portions of the trial are presented in [Flow Chart 1](#) (dose escalation) and [Flow Chart 2](#) (dose expansion) of this protocol. The key procedures required include:

- PK samples throughout the trial
- Reporting of all AEs occurring after the ICF has been signed
- Baseline and on-treatment blood biomarker and immunogenicity assessments
- Tumour biopsy biomarker assessments
- Tumour assessments (based on CT/PET and/or MRI scan) according to RECIST Version 1.1 and iRECIST must be performed once every 2 cycles (meaning every 6 weeks if there are no delays in cycles but as close as possible to the end of the second of the 2 cycles of treatment if there was a delay) after the start of BI 754091.

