## **2 LIST OF ABBREVIATIONS**

See Medicine Glossary:

<http://glossary>

Term	Definition / description
ADA	Anti-Drug Antibody
AE	Adverse Event
AESI	Adverse Event of Special Interest
ALT	Alanine aminotransferase
ANCOVA	Analysis of Covariance
AST	Aspartate aminotransferase
ATC	Anatomical Therapeutic Chemical
AUC	Area Under the Curve
CI	Confidence Interval
CR	Complete Response
CT	Comcomitant Therapy
CTCAE	Common Terminology Criteria for Adverse Events
CTP	Clinical Trial Protocol
CTR	Clinical Trial Report
DCR	Disease Control Rate
DLT	Dose Limiting Toxicity
DoR	Duration of Response
ECG	Electrocardiogram
ECOG	Eastern Cooperative Oncology Group
eCRF	Electronic Case Report Form
EOT	End of Treatment
ICH	International Conference on Harmonisation
iCPD	Immune Confirmed Progressive Disease
iCR	Immune Complete Response
iORR	Immune Objective Response Rate
iPFS	Immune Progression-Free Survival
iPR	Immune Partial Response
iRECIST	Immune Response Evaluation Criteria in Solid Tumours

Term	Definition / description
iSD	Immune Stable Disease
iUPD	Immune Unconfirmed Progressive Disease
LLT	Lowest Level Term
Max	Maximum
MedDRA	Medical Dictionary for Regulatory Activities
Min	Minimum
MTD	Maximum Tolerated Dose
NE	Not Evaluable
OR	Objective Response
ORR	Objective Response Rate
OS	Overall Survival
PBMC	Peripheral Blood Mononuclear Cell
P25	25 th percentile
P75	75 th percentile
PD	Progressive Disease
PD	Protocol Deviation
PDc	Pharmacodynamics
PFS	Progression-Free Survival
PK	Pharmacokinetics
PKS	Pharmacokinetics Analysis Set
PR	Partial Response
PT	Preferred Term
Q1	Lower quartile
Q3	Upper quartile
P10	10th percentile
P90	90th percentile
RECIST	Response Evaluation Criteria in Solid Tumours
REP	Residual Effect Period
RO	Receptor Occupancy
RP2D	Recommended Phase 2 Dose
RPM	Report Planning Meeting
SAE	Serious Adverse Event

Term	Definition / description
SD	Stable Disease
StD	Standard Deviation
SOC	System Organ Class
TNBC	Triple Negative Breast Cancer
TS	Treated Set
TSAP	Trial Statistical Analysis Plan
WHO DD	World Health Organization Drug Dictionary

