## **5. ENDPOINTS(S)**

### **5.1 PRIMARY ENDPOINT(S)**

The primary objective of this study is to determine the safety and tolerability of BI 754091 as reflected by the primary endpoint MTD.

The primary endpoint of the Phase Ia dose-escalation portion of the trial is:

- Number of patients experiencing Dose Limiting Toxicities (DLTs) graded according to CTCAE Version 4.03, observed in the first cycle (3 weeks) in order to meet the objective of assessment of the MTD of BI 754091.

The number of patients with DLTs during the MTD evaluation period will be used to determine the MTD. The MTD is defined as the highest dose with less than 25% risk of the true DLT rate being above 33% during MTD evaluation period. For definition of DLTs, see CTP Section 4.1.5. The MTD evaluation period is defined as the first three weeks after a first administration of trial medication to BI 754091.

Patients who were replaced during the MTD evaluation period will not be considered for MTD determination. Those patients that have completed the MTD evaluation period without having been replaced will be referred to as patients evaluable for MTD determination (MTD set).

In addition, the primary endpoints of the Phase Ib dose-expansion portion of the trial are:

- Number of patients with DLTs observed during the entire treatment period, from the first infusion of study treatment to the date of last study treatment administration plus 30 days. See treatment period definition in [Table 6:1:1](#).
- Confirmed objective Response (OR), defined as the best overall response of confirmed complete response (CR) or partial response (PR) according to RECIST v1.1 assessed by the Investigator, where the best overall response is the best time point response recorded from the first administration of BI 754091 until the earliest of disease progression according to RECIST v1.1, death or last evaluable tumor assessment before start of subsequent anti-cancer therapy, loss to follow- up or withdrawal of consent.

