**PFS according to RECIST v1.1:**

For patients with 'event' as outcome for PFS:

- PFS [days] = date of outcome – date of first treatment administration + 1

For patients with 'censored' as outcome for PFS:

- PFS (censored) [days] = date of outcome – date of first treatment administration + 1

A patient has an evaluable response assessment if CR, PR, stable disease (SD), or progressive disease (PD) according to RECIST v1.1 has been assigned by the investigator. The censoring rules and applicable dates of outcome are specified in Table 5.2.2.2: 1 below.

If patients would have their radiological examinations over a number of days, i.e. target lesions assessed on day x, non-target lesions assessed on day y and new lesion (if applicable) on day z, the earliest date of the multiple assessments should be considered.

Table 5.2.2.2: 1 Censoring rules for progression-free survival according to RECIST v1.1

Situation	Outcome	Date of outcome
No baseline radiological assessment		
Patient with death on or before first planned post-baseline radiological assessment ( $\leq$ Day 64)	Event	Date of death
Patient without death or patient with death after first planned post-baseline radiological assessment ( $>$ Day 64)	Censored	First treatment administration
Without post-baseline radiological assessments		
Vital status is unknown or patient is known to be alive	Censored	First treatment administration
Death prior to or on the first planned post-baseline radiological assessment ( $\leq$ Day 64)	Event	Date of death
Death beyond the first planned post-baseline radiological assessment ( $>$ Day 64)	Censored	First treatment administration
With baseline and post-baseline radiological assessments BUT no other anti-cancer therapy		
Alive and not progressed	Censored	Date of last evaluable radiological assessment
Progressed, no missed radiological assessment window* prior to progression	Event	Date of radiological assessment of progression

Table 5.2.2.2: 1 Censoring rules for progression-free survival according to RECIST v1.1  
(cont.)

Situation	Outcome	Date of outcome
Progressed, but one or more consecutively missed radiological assessment window* prior to progression	Censored	Date of last evaluable radiological assessment prior to missed assessment (or first treatment administration if no post-baseline assessment prior to missed assessment)

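### Below the 39-day minimum, the SAP's confirmed best-response table labels PR-then-SD and SD-then-SD patients as PD although no scan shows progression

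*SAP*

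**What the plan says.** SAP Section 5.2.2.1, Table 5.2.2.1: 1 crosses the response at a first time point with the response at least 28 days later.

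- For PR then SD, the confirmed best response is "SD as long as >=39 days*, otherwise, PD". The same cell text stands against CR then PD, against PR then PD, and against one merged row that covers both SD then SD and SD then PD.
- For CR, PR or SD followed by a non-evaluable or missing assessment, the cell reads "SD as long as >=39 days*, otherwise, NE".
- The footnote to the 39 days says only "after first treatment administration". It does not say whether the first or the second assessment has to reach that day.

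Three other rules bear on this:

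- SAP Section 5.1 says that "the best overall response is the best time point response recorded from the first administration of BI 754091", up to progression or the other listed end points.
- SAP Table 5.2.2.2: 1 censors for PFS a patient who is "Alive and not progressed", given baseline and post-baseline imaging and no other anti-cancer therapy.
- The protocol (Flow Chart 2, footnote m) schedules scans "every 2 cycles (6 weeks) for the first 6 months of treatment". SAP Table 6.7: 1 puts the first due date at Day 43, with first dose as Day 1.

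**The concern.** A PD fallback makes sense when the second assessment is PD: stable disease was not held long enough to count, and progression followed. It makes no sense when the second assessment is SD, because nothing on file shows progression. Merging SD-SD with SD-PD in one row carries the PD fallback over to SD-SD, and the PR-SD row has the same wording.

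The result conflicts with the SAP in three places. PD cannot be the best of two SD assessments, or of PR and SD, under the Section 5.1 definition. A patient with a later non-PD scan is ranked below a patient with no later scan (PD against NE). And one patient can be PD in the best-response table while counted as not progressed for PFS. At stake is the reported distribution of best overall response in each cohort.

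**Working it through.** **Which cells are wrong.** Reading the table as a lookup, the pairs that can return PD without a PD input are:

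| First assessment | Second assessment | Minimum met | Minimum not met |
|---|---|---|---|
| PR | SD | SD | PD |
| SD | SD | SD | PD |

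No other pair does this. For comparison, PR or SD followed by a missing scan gives SD or NE.

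**When the branch is reached.** First dose is Day 1 (SAP Section 6.7), so days after first dose = study day − 1.

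- The minimum of 39 days after first dose falls on study Day 39 + 1 = Day 40.
- The due date, Day 43, is 43 − 1 = 42 days after first dose. The slack is 42 − 39 = 3 days, so a scan 4 or more days early misses the minimum.

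*Clock read at the first assessment.* The branch applies if the first scan is on Day 39 or earlier (38 days or fewer after first dose). It does not apply from Day 40 on.

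*Clock read at the second assessment.* The second scan must be on Day 39 or earlier and at least 28 days after the first. The first is then on Day 39 − 28 = Day 11 or earlier.

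**Examples with the second scan on Day 85.**

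| First scan | Pair | Clock at first | Clock at second |
|---|---|---|---|
| Day 36 | SD, SD | PD | SD |
| Day 36 | PR, SD | PD | SD |
| Day 36 | SD, missing | NE | – |
| Day 39 | SD, SD | PD | SD |
| Day 40 | SD, SD | SD | SD |
| Day 43 | SD, SD | SD | SD |

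The first and third rows show the inversion: the added SD scan turns NE into PD.

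**Can early scans occur?** Yes, outside the schedule. SAP Section 6.7 assigns images from the first three weeks to Week 6. The protocol allows assessments at the Investigator's discretion. Protocol Section 6.2.3.1 requires imaging when treatment stops without PD, unless a scan was done in the past 4 weeks, and Section 5.2.1 continues assessment afterwards. A patient who stops early could have SD at an early end-of-treatment scan and SD again later.

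**Effect on results.** SAP Section 7.4.1 counts only CR and PR in ORR. SD, PD and NE are all non-response, so the change in confirmed ORR is 0. Each misclassified patient shifts the best-response distribution by 1/30 = 3.3 percentage points in a group of 30.

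**The case against.** The strongest reply is that the branch will rarely be used. The first scan is due on Day 43, and even if the flow chart's ±2-day visit window is applied to it, the earliest day is Day 41, which gives SD under both readings. Under the second-assessment reading, both scans would fall inside the Week 6 imaging window (Days 1 to 64). SAP Section 6.7 keeps the last image in a window when presenting response data; if that also governs this derivation, the second-assessment route closes. A programmer who applies the table to every scan pair and keeps the best result would also rescue many patients: SD on Day 85 followed by a missing scan gives SD. All of this stands as a limit on the number affected. It does not make the cells right, and the SAP states neither of the last two rules for this table.

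Four stronger readings are tempting, and the documents do not support them.

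- *Non-progressors in general are reported as PD.* No; the 39-day condition is decisive.
- *The disease control rate is biased downward.* In the readable SAP, "Disease Control Rate" appears only in the abbreviation list, and parts of the SAP are redacted. Whether it is derived from this table cannot be seen.
- *The protocol invites early scanning.* The wording "as close as possible to the end of the second of the 2 cycles of treatment" in Protocol Section 6.2 applies when cycles were delayed, which moves scans later and away from this branch.
- *The missing CR-then-PR and CR-then-SD rows put ORR at risk.* Those rows are absent, but this is missing detail rather than a wrong rule. If such pairs were treated like CR then PD, they would be non-response. Letting the Investigator re-read an earlier CR as PR would add retrospective discretion to an open-label primary endpoint, and nothing in the documents provides for it.

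**Conclusion.** The point holds in a narrow form. Two input pairs, PR-SD and SD-SD, return PD without evidence of progression when the 39-day minimum is missed. This conflicts with the SAP's own definition of best overall response, with the NE fallback in the same table and with the PFS censoring rule. The trigger is a first scan on Day 39 or earlier, or on Day 11 or earlier, depending on a reference point that the table leaves open.

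Few patients are likely to be affected. That is a judgement resting on scans being done close to schedule; the documents give no scan-timing data. Confirmed ORR does not change. Only the SD/PD/NE split of best overall response is affected. A wrong cell that costs almost nothing to correct should still be corrected.

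**What to change.** In SAP Table 5.2.2.1: 1:

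1. Split the merged row into SD then SD and SD then PD.
2. For SD then SD and for PR then SD, make NE the fallback when the minimum is not met. Keep PD as the fallback only where the second assessment is PD.
3. State in the footnote that the 39-day minimum is met if any non-PD assessment is made at least 39 days after first dose.

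Changes 2 and 3 do different things. Change 2 alone moves patients from PD to NE and adds nobody to SD. Change 3 moves a patient with SD on Day 36 and Day 85 to SD, leaving the NE fallback for patients whose scans all precede Day 40.

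The cost is a few cells, one footnote and the matching program. No new data are needed.

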### 5.2.2.2 Secondary endpoints of the Phase Ib (dose expansion) of the trial

The secondary endpoints of the Phase Ib dose-expansion portion of the trial are:

- Progression-free survival (PFS) defined from date of start administration of BI 754091 to the date of disease progression according to RECIST v1.1 as assessed by the Investigator or death from any cause, whichever is earlier
- Safety will continue to be assessed by the recording of adverse events (AEs), serious adverse events (SAEs) (including DLTs), laboratory evaluations, vital signs, and ECGs as:
  - Percentage of subjects with AEs
  - Percentage of subject with SAEs
  - Percentage of subjects with clinical relevant abnormalities in vital signs, laboratory evaluations or ECG parameters (note that clinically relevant abnormalities are those which have to be reported by the investigator as AEs).

**PFS according to RECIST v1.1:**

For patients with 'event' as outcome for PFS:

- PFS [days] = date of outcome – date of first treatment administration + 1

For patients with 'censored' as outcome for PFS:

- PFS (censored) [days] = date of outcome – date of first treatment administration + 1

A patient has an evaluable response assessment if CR, PR, stable disease (SD), or progressive disease (PD) according to RECIST v1.1 has been assigned by the investigator. The censoring rules and applicable dates of outcome are specified in Table 5.2.2.2: 1 below.

If patients would have their radiological examinations over a number of days, i.e. target lesions assessed on day x, non-target lesions assessed on day y and new lesion (if applicable) on day z, the earliest date of the multiple assessments should be considered.

Table 5.2.2.2: 1 Censoring rules for progression-free survival according to RECIST v1.1

Situation	Outcome	Date of outcome
No baseline radiological assessment		
Patient with death on or before first planned post-baseline radiological assessment ( $\leq$ Day 64)	Event	Date of death
Patient without death or patient with death after first planned post-baseline radiological assessment ( $>$ Day 64)	Censored	First treatment administration
Without post-baseline radiological assessments		
Vital status is unknown or patient is known to be alive	Censored	First treatment administration
Death prior to or on the first planned post-baseline radiological assessment ( $\leq$ Day 64)	Event	Date of death
Death beyond the first planned post-baseline radiological assessment ( $>$ Day 64)	Censored	First treatment administration
With baseline and post-baseline radiological assessments BUT no other anti-cancer therapy		
Alive and not progressed	Censored	Date of last evaluable radiological assessment
Progressed, no missed radiological assessment window* prior to progression	Event	Date of radiological assessment of progression

Table 5.2.2.2: 1 Censoring rules for progression-free survival according to RECIST v1.1  
(cont.)

Situation	Outcome	Date of outcome
Progressed, but one or more consecutively missed radiological assessment window* prior to progression	Censored	Date of last evaluable radiological assessment prior to missed assessment (or first treatment administration if no post-baseline assessment prior to missed assessment)
Death but no progression, no missed radiological assessment window* prior to death	Event	Date of death
Death without progression, but one or more consecutively missed radiological assessment window* prior to death	Censored	Date of last evaluable radiological assessment prior to missed assessments
Initiation of subsequent anti-cancer therapy		
Subsequent anti-cancer therapy started before progression or death	Censored	Date of last radiological assessment before subsequent anti-cancer therapy
No baseline and/or post-baseline imaging and subsequent anti-cancer therapy started prior to death	Censored	First treatment administration

\* Windows for radiological assessments are defined in [Table 6.7: 1](#)

[figure not shown]

---

Proprietary confidential information © 2021 Boehringer Ingelheim International GmbH or one or more of its affiliated companies

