#### Imaging time windows:

Time windows and visits will be calculated to determine the planned day of tumour measurement and response status, based on the protocol-specified tumour imaging schedule.

For the presentation of tumour response data which will follow a calculated visit approach

based on the protocol specified tumour imaging schedule. Imaging will be performed at screening and every 6 weeks after BI 754091 infusion (i.e. Week 6, 12, 18 ...etc.), then every 9 weeks after 6 months of treatment; image data will be slotted to Week 6, 12, 18 etc. based on their relative day (from start of treatment) and using a  $\pm 3$  week window (images taken in the first 3 weeks from start of treatment will be assigned to Week 6). If two or more images for a patient are assigned to one interval then the last assessment will be used to ensure progressive disease is not missed.

In order to identify whether consecutive imaging time points are missing for a given patient, a nominal time point (i.e. Week 6, 12, 18 ... etc.) will be assigned to each and every image. This is achieved by creating windows for every radiological response assessment. These windows are defined in [Table 6.7: 1](#).

Table 6.7: 1 Nominal time points and windows for imaging

Nominal time point (weeks from start of study medication)	Due date of scans (days)*	Window (days)
6	43	1 to $\leq$ 64
12	85	65 to $\leq$ 106
18	127	107 to $\leq$ 148
24	169	149 to $\leq$ 200
33	232	201 to $\leq$ 263
42	295	264 to $\leq$ 326
51	358	327 to $\leq$ 389
Etc., 9 week interval	Etc.	Etc.

\* The date of the first dose of study medication is Day 1

If a patient does not have an image in one of the windows described above, he/she will be considered to have missed an assessment for that time point.

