## **7. PLANNED ANALYSIS**

For End-Of-Text (EoT) tables, the set of summary statistics is: N / Mean / Standard deviation (StD) / Min / Median / Max.

For tables that are provided for endpoints with some extreme data, median, quartiles and percentiles should be preferred to Mean, StD, Min and Max.

For time-to-event analysis tables the set of statistics is: number of patients [N(%)], number of patients with event [N(%)], <time to event> [months] followed by P25 (25th percentile), median, P75 (75th percentile) and number of patients censored [N(%)]. If not specified otherwise the duration as well as the time to event will be displayed in months.

Tabulations of frequencies for categorical data will include all possible categories and will display the number of observations in a category as well as the percentage (%) relative to the respective treatment group (unless otherwise specified, all patients in the respective patient set whether they have non-missing values or not). Percentages will be rounded to one decimal place. The category missing will be displayed only if there are actually missing values.

Sort order for general categorical variables: If categories correspond to the collected categories on the eCRF and the table shells do not explicitly specify the ordering, the “default ordering” defined by the eCRF is to be used in such cases. If categories are derived, the ordering as specified in the table shell document should be used; in general ordinal data (e.g. categorised continuous data) are to be displayed in ascending order. Abbreviations (e.g. Wors.) should not be displayed without any explanations. They will be either spelled out in the table or explained in footnotes (whatever is more reasonable from the programming point of view).

If applicable, conversion from days to weeks, months and years will be as follows:

- Weeks = Days / 7
- Months = (Days \* 12) / 365.25
- Years = Days / 365.25

[REDACTED] history, prior anti-cancer therapies, medical history and baseline disease assessment.

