**7.5.2.2 Phase Ib**

*Progression-free survival by RECIST 1.1*

PFS will be summarized descriptively by quartiles with 95% confidence interval (based on the Greenwood's method) calculated from Kaplan-Meier estimate.

*Safety*

Number of patients with AEs, SAEs and clinical relevant abnormalities in vital signs, laboratory evaluations or ECG parameters as reported by the investigator as AEs will be summaries for each cohort.

Please refer to [Section 7.5.2.1](#).

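### PFS censors a progression or death after one empty calendar-day imaging window, although the protocol moves scans with delayed cycles, so genuine events can be lost

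*SAP*

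**What the plan says.** **SAP 5.2.2.2** defines PFS as time to RECIST v1.1 progression or death from any cause. Table 5.2.2.2:1 then sets these rules:

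- "Progressed, but one or more consecutively missed radiological assessment window* prior to progression": censored at the last evaluable scan before the gap, or at first dose if there is none.
- "Death without progression, but one or more consecutively missed radiological assessment window* prior to death": censored at the last evaluable scan before the gap.
- No post-baseline scan and "Death beyond the first planned post-baseline radiological assessment" (after Day 64): censored at first dose.
- "Alive and not progressed": censored at the last evaluable scan, with no missed-window condition.

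**SAP 6.7** gives the purpose of the windows: "In order to identify whether consecutive imaging time points are missing for a given patient". It defines a miss by calendar days alone: "If a patient does not have an image in one of the windows described above, he/she will be considered to have missed an assessment".

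**Protocol 6.2** ties scans to every second cycle. They fall six-weekly if nothing is delayed, and otherwise as near as possible to the end of the second cycle. **Protocol 4.1.4** lets a dose be delayed by up to 6 weeks for AEs. The flow charts print only a 6-weekly, later 9-weekly, interval. After treatment stops without PD, **Protocol 5.2.1** leaves imaging to standard of care. **Protocol 7.3.2** leaves the censoring rules to the SAP.

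**SAP 7.5.2.2** states: "PFS will be summarized descriptively by quartiles with 95% confidence interval". The time-to-event tables in SAP 7 also report the numbers of patients with an event and censored.

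**The concern.** The protocol's scan calendar moves with treatment and the SAP's does not. A patient scanned exactly as Protocol 6.2 requires can therefore be recorded as having missed an assessment, and a PD documented at that scan drops out of the endpoint. Deaths need no scan to be dated, yet they are cut back by the same mechanism.

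The trigger of one also fits poorly with the SAP's stated aim of finding consecutive missing time points. Nor does the SAP say whether an earlier empty window, followed by an evaluable scan, still triggers censoring. Two programmers could produce different event counts from the same data.

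No test or decision rule depends on PFS. At stake are the event and censored counts, which change with every lost event, and the P25, median and P75, which can change.

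**Working it through.** **1. Reproducing Table 6.7:1.** Due day = 7 × week + 1. Upper limit = midpoint to the next due day, rounded down: (43+85)/2 = 64; (85+127)/2 = 106; (127+169)/2 = 148; (169+232)/2 = 200.5, so 200; (232+295)/2 = 263.5, so 263. All seven rows match.

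**2. Slack in each window.** Upper limit minus due day is 64−43 = 106−85 = 148−127 = 21 days. From Week 24 it is 200−169 = 263−232 = 31 days. The smallest cumulative delay that empties a window is therefore 22 days for scans due on Day 43, 85 or 127, and 32 days afterwards. Six weeks is 42 days, so both lie within one permitted delay.

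**3. Applying Table 5.2.2.2:1.**

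| Situation | Empty window | PFS outcome |
|---|---|---|
| First scan 28 days late (Day 71), PD | 1-64 | Censored at first dose |
| Scan Day 43, next 22 days late (Day 107), PD | 65-106 | Censored at Day 43 |
| Each cycle 7 days late: scans Days 57 and 113, PD on Day 113 | 65-106 | Censored at Day 57 |
| Off treatment, scans 84 days apart (assumed): Days 43 and 127, PD on Day 127 | 65-106 | Censored at Day 43 |
| Scan Day 43, no image Days 65-106, death Day 110 | 65-106 | Censored at Day 43 |
| No post-baseline scan, death Day 80 | 1-64 | Censored at first dose |

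**4. Size, by simulation under assumptions.** PFS is exponential with median 85 or 120 days, and PD is found at the next scheduled scan. There are no extra scans, follow-up is 380 days, and a delayed patient has one delay. There were 200,000 patients per setting.

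| Patients delayed, length | Gap that counts | Events lost | 6-month PFS (points) |
|---|---|---|---|
| 10%-20%, 1-42 d | just before PD | 1.2%-3.5% | +0.4 to +1.3 |
| 10%-20%, 1-42 d | any earlier | 2.5%-7.5% | 0 to +0.6 |
| 10%-20%, 22-42 d | just before PD | 2.4%-6.9% | +0.8 to +2.8 |
| 10%-20%, 22-42 d | any earlier | 5.0%-14.9% | 0 to +1.3 |
| 2%-5%, 22-42 d | just before PD | 0.5%-1.7% | +0.2 to +0.7 |

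For scale, the standard error of 6-month PFS with 30 patients is about √(0.333 × 0.667/30) = 8.6 points.

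In simulated cohorts of 30 (delays 1-42 days, 10%-20% delayed, gap just before PD), at least one event was lost in 28%-62% of cohorts. P25 changed in 1%-7%, the median in 5%-25% and P75 in 2%-12%. If any earlier gap counts, P75 changed in 8%-24%, in either direction. In the large-sample runs P25 never moved, and the median and P75 moved only in some settings.

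A separate simulation used heavier, recurring delays: 7-42 days in 5%-20% of scan intervals, 15% of events deaths, any earlier gap counting. The share of patients with an event fell from about 100% to 92%-71% (median 3 months), or from about 94% to 84%-57% (median 6 months). Six-month PFS there was 0.5 to 2.0 points lower than when all events counted.

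**5. Deaths, one hypothetical cohort of 30.** Events: 8 at Day 43, 4 at Day 85, 4 on Days 110-127, 4 at Day 169. With all events counted, 6-month PFS = 10/30 = 33.3% and the median is Day 120.

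- Day 110 death censored at Day 43: 22/30 × 17/21 × 14/17 × 10/14 = 34.9%; median Day 127.
- One Day 85 event replaced by a Day 80 death without a scan, censored at first dose: 10/29 = 34.5%; median Day 127.

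**6. Two-window rule.** The delay before one scan that empties two windows in a row is 107−43 = 149−85 = 64 days, 201−127 = 74 days, or 264−169 = 95 days. All exceed 42. A single delay of up to 42 days empties at most one window over the whole course. In the step 4 simulation the rule lost 0.0% of events in every setting.

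**The case against.** The protocol delegates the censoring rules, and the SAP states its one-window rule explicitly and applies it to PD and death alike. One missed window against two is an analyst's choice. Read literally, any empty window before progression counts, and on that reading 6-month PFS hardly moves in the single-delay simulation. Even on the other reading the shift is small beside the standard error. With 2%-5% of patients delayed, about half an event at most is lost in a cohort of 30 (1.7% × 30 = 0.5). The simulations ignore discretionary scans and the scan required at discontinuation without PD, which would fill some windows. If 6 weeks means the interval between doses, one delay puts the first scan on Day 64, inside its window. The median in the death example sits exactly on 0.500; with 6 events at Day 43 instead of 8 it would not move. Robustness analyses may be in redacted text.

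Much of this stands. The effect on the curve is modest, its direction is not fixed if any earlier gap counts, and the death example shows a possibility only. Censoring a living, progression-free patient at the last evaluable scan is reasonable in itself. What does not fall away is the mismatch. The right to choose a rule does not make a protocol-compliant scan a missed one. Accumulated delays and standard-of-care imaging off treatment still lose events under the interval reading of 6 weeks, and dated deaths are lost whatever the cycle timing.

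**Conclusion.** The concern holds. A fixed-day window combined with a trigger of one removes documented progressions and dated deaths from an endpoint defined as progression or death from any cause. The thresholds (22 and 32 days, and the Day 64 and Day 106 limits for deaths) follow directly from the documents.

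The frequency does not. With 10%-20% of patients delayed once by 1-42 days, about 1%-4% of events are lost if only the gap just before PD counts, and 3%-8% if any earlier gap counts. Heavier or recurring delays lose more. If only the last gap counts, PFS is shifted upward. If any earlier gap counts, the simulated 6-month estimate rose slightly or fell, depending on the delay pattern. These sizes rest on assumed delay rates, exponential PFS and no extra scans. Since PFS is secondary, descriptive and untested, this should be corrected but does not threaten the trial's main conclusions.

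**What to change.** In SAP Table 5.2.2.2:1:

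- Censor a PD or death only when two or more consecutive windows immediately before it are empty. A death after a Day 43 scan then counts as an event up to Day 148 instead of Day 106.
- Give deaths without a post-baseline scan the same allowance: an event up to Day 106 instead of Day 64.
- State that an earlier empty window followed by an evaluable scan does not trigger censoring.

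Table 6.7:1 can stay as it is. Unless the redacted text already contains one, add a sensitivity analysis that counts every documented PD or death as an event.

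The cost is wording in one table and minor reprogramming. The downside is slightly more uncertainty in the dating of some progressions, because a PD found after one empty window is now kept.
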